## **Last contact date**

The last contact date will be used for censoring of subjects in the analysis of overall survival.

The last contact date is defined as the latest complete date from the below list on or before the data cut-off date ([Table 5-1](#)). The cut-off date will not be used for last contact date, unless the subject was seen or contacted on that date. No date post cut-off date will be used.

Completely imputed dates (e.g., the analysis cut-off date programmatically imputed to replace the missing end date of a dose record) will not be used to derive the last contact date. Partial date imputation is allowed for event (death)/censoring only if coming from the 'Survival' eCRF.

The last contact date will be derived for subjects not known to have died at the analysis cut-off using the last complete date among the following:

**Table 5-1      Last contact date data sources**

Source data	Conditions
Date of Randomization	No condition
Last date subject was known to be alive from Survival Follow-up page	Subject status is reported to be alive or unknown
Start/End dates from further antineoplastic therapy	Non-missing medication/procedure term
Start/End dates from drug administration record	Non-missing dose
Response assessment date	Response marked as 'done'
Laboratory/PK collection dates	Sample collection marked as 'done'
Vital signs date	At least one non-missing parameter value
ECOG performance status date	Non-missing performance status
Start/End dates of AE	Non-missing verbatim term

## 5.2 Statistical models

### 5.2.1 ELN risk stratification categories

Sub-classification of AML subjects will be categorized by using the ELN 2017 risk stratification ([Döhner et al 2017](#)) and ELN 2022 risk stratification ([Döhner et al 2022](#)).

ELN risks will be derived based on the following rules: for each subject,

- 1) If he/she has any favorable genetic abnormality (cytogenetic or molecular genetic), a "Favorable" risk will be assigned. That is, Favorable genetic abnormalities always took precedence.
- 2) Then, if he/she has any adverse genetic abnormality (cytogenetic or molecular genetic), an "Adverse" risk will be assigned.

- 3) Then, if he/she has any intermediate genetic abnormality (cytogenetic or molecular genetic), an “Intermediate” risk will be assigned.
- 4) Then, if he/she has no cytogenetic and molecular genetic assessments, a “Missing” risk will be assigned; Otherwise, an “Intermediate” risk will be assigned.

Table 5-2 2017 ELN risk stratification by geneticsa

Risk Category b	Genetic Abnormality
Favorable	
 
• t(8;21)(q22;q22.1); RUNX1-RUNX1T1
 
• inv(16)(p13.1q22) or t(16;16)(p13.1;q22); CBFB-MYH11
 
• Mutated NPM1 without FLT3-ITD or with FLT3-ITDlow(c)
 
• Biallelic mutated CEBPA
 

Intermediate	
 
• Mutated NPM1 and FLT3-ITDhigh(c)
 
• Wild type NPM1 without FLT3-ITD or with FLT3-ITDlow(c) (w/o adverse-risk genetic lesions)
 
• t(9;11)(p21.3;q23.3); MLLT3-KMT2Ad
 
• Cytogenetic abnormalities not classified as favorable or adverse
 

Adverse	
 
• t(6;9)(p23;q34.1); DEK-NUP214
 
• t(v;11q23.3); KMT2A rearranged
 
• t(9;22)(q34.1;q11.2); BCR-ABL1
 
• inv(3)(q21.3q26.2) or t(3;3)(q21.3;q26.2); GATA2,MECOM(EVI1)
 
• -5 or del(5q); -7; -17/abn(17p)
 
• Complex karyotypee, monosomal karyotypef
 
• Wild type NPM1 and FLT3-ITDhigh(c)
 
• Mutated RUNX1g
 
• Mutated ASXL1g
 
• Mutated TP53h
 

a. Frequencies, response rates and outcome measures should be reported by risk category, and, if sufficient numbers are available, by specific genetic lesions indicated.

b. Prognostic impact of a marker is treatment-dependent and may change with new therapies.

c. Low, low allelic ratio (<0.5); high, high allelic ratio ( $\geq 0.5$ ); semi-quantitative assessment of *FLT3-ITD* allelic ratio (using DNA fragment analysis) is determined as ratio of the area under the curve (AUC) "*FLT3-ITD*" divided by AUC "*FLT3-wild type*"; recent studies indicate that acute myeloid leukemia with *NPM1* mutation and *FLT3-ITD* low allelic ratio may also have a more favorable prognosis and patients should not routinely be assigned to allogeneic hematopoietic-cell transplantation.

d. The presence of t(9;11)(p21.3;q23.3) takes precedence over rare, concurrent adverse-risk gene mutations.

e. Three or more unrelated chromosome abnormalities in the absence of one of the World Health Organization-designated recurring translocations or inversions, i.e., t(8;21), inv(16) or t(16;16), t(9;11), t(v;11)(v;q23.3), t(6;9), inv(3) or t(3;3); AML with *BCR-ABL1*.

f. Defined by the presence of one single monosomy (excluding loss of X or Y) in association with at least one additional monosomy or structural chromosome abnormality (excluding core-binding factor AML).

g. These markers should not be used as an adverse prognostic marker if they co-occur with favorable-risk AML subtypes.

h. *TP53* mutations are significantly associated with AML with complex and monosomal karyotype.

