## 1. Introduction

This statistical analysis plan (SAP) describes the planned analyses for the final Clinical Study Report (CSR) of the study CMBG453C12201, a phase II, open-label, single-arm, multi-center study of MBG453 in combination with azacitidine and venetoclax in adult subjects with newly diagnosed AML, who are not suitable for intensive chemotherapy and not planned for hematopoietic stem cell transplantation (HSCT).

As specified in the Section 12.7 of the study protocol, safety meetings were conducted during the safety run-in part of the study to assess the tolerability of MBG453 at two different doses (400 mg and 800 mg administered every 4 weeks) when given together with azacitidine + venetoclax before enrolling subject in the expansion part of the study. This SAP served as the basis for those analyses as well; however, a separate selection of tables, figures and listings (TFL) was done. In the meetings (one held on 22-Mar-2021, another on 26-Oct-2021), steering committee members agreed that there is no safety concern identified with the combination of MBG453 (400 mg or 800mg) with azacitidine and venetoclax, then MBG453 800 mg expansion cohort was opened and a total of 85 patients were enrolled and treated at 800 mg MBG453 (including those in safety run-in part).

[figure not shown]
The content of this SAP is based on the CMBG453C12201 protocol, Amendment 5 (08-Dec-2022). All decisions regarding the analysis, as defined in the SAP document, have been made prior to database lock.

However, Novartis made the decision in December 2023 to early terminate the sabatolimab (MBG453) clinical development program following the results of the primary analyses of phase II STIMULUS MDS1 and Phase III STIMULUS MDS2 studies – both studies failed to meet their primary objectives. As a consequence, this study was decided to be early terminated and the investigator letter about this decision was sent on 11-Jan-2024. Based on this decision, the primary analysis of CR rate after 12 cycles will be skipped, and the study data will be analyzed and reported based on all data up to final database lock (DBL) in the final CSR. This also meets the regulatory requirements.

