## 2.3 Patient disposition, demographics, and other baseline characteristics

The FAS will be used for the analyses below. Patient disposition, demographics and other baseline characteristics will be summarized by dose level of MBG453 (400 mg Q4W, 800 mg Q4W) and for all subjects (“All subjects” column).

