### **2.3.2 Demographic and other baseline characteristics**

Demographic and other baseline data including disease characteristics will be listed and summarized descriptively for all subjects from the FAS.

BMI (kg/m^2) at baseline will be calculated as weight[kg] / (height[m]) using weight at baseline and height at screening. Body Surface Area (BSA) is based on the Mosteller formula described in [Section 2.4.1](#).

Details on AML diagnosis (initial diagnosis, ELN 2017 risk classification ([Döhner et al 2017](#)), current disease status (de novo or secondary) and cytogenetic abnormalities will be tabulated and time since diagnosis will be summarized.

Relevant medical histories and current medical conditions at baseline will be summarized by system organ class and preferred term. Medical history and current medical conditions will be coded using the Medical Dictionary for Regulatory Activities (MedDRA) terminology. The MedDRA version used for reporting will be specified in the CSR and as a footnote in the applicable outputs. Comorbidities at baseline that exclude subjects from receiving intensive chemotherapy (presence of specific cardiac, pulmonary, hepatic or renal comorbidities) will be summarized by age category (<75 years old and  $\geq$  75 years old).

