**Table 5-3 2022 ELN risk stratification by genetics at initial diagnosisa**

Risk Category b	Genetic Abnormality
Favorable	
 
• t(8;21)(q22;q22.1)/RUNX1::RUNX1b,c
 
• inv(16)(p13.1q22) or t(16;16)(p13.1;q22)/CBFB::MYH11b,c
 
• Mutated NPM1b,d without FLT3-ITD
 
• bZIP in-frame mutated CEBPAe
 

Intermediate	
 
• Mutated NPM1b,d with FLT3-ITD
 
• Wild-type NPM1 with FLT3-ITD
 
• t(9;11)(p21.3;q23.3)/MLLT3::KMT2Ab,f
 
• Cytogenetic and/or molecular abnormalities not classified as favorable or adverse
 

Adverse	
 
• t(6;9)(p23;q34.1)/DEK::NUP214
 
• t(v;11q23.3)/KMT2A-rearrangedg
 
• t(9;22)(q34.1;q11.2)/BCR::ABL1
 
• t(8;16)(p11;p13)/KAT6A::CREBBP
 
• inv(3)(q21.3q26.2) or t(3;3)(q21.3;q26.2)/GATA2, MECOM(EVI1)
 
• t(3q26.2;v)/MECOM(EVI1)-rearranged
 
• -5 or del(5q); -7; -17/abn(17p)
 
• Complex karyotype,h monosomal karyotypei
 
• Mutated ASXL1, BCOR, EZH2, RUNX1, SF3B1, SRSF2, STAG2, U2AF1, or ZRSR2j
 
• Mutated TP53k
 

a. Frequencies, response rates and outcome measures should be reported by risk category, and, if sufficient numbers are available, by specific genetic lesions indicated.

b. Mainly based on results observed in intensively treated patients. Initial risk assignment may change during the treatment course based on the results from analyses of measurable residual disease.

c. Concurrent of KIT and/or FLT3 gene mutation does not alter risk categorization.

d. AML with NPM1 mutation and adverse-risk cytogenetic abnormalities are categorized as adverse-risk.

e. Only in-frame mutations affecting the basic leucine zipper (bZIP) region of CEBPA, irrespective whether they occur as monoallelic or biallelic mutations, have been associated with favorable outcome.

f. The presence of t(9;11)(p21.3;q23.3) takes precedence over rare, concurrent adverse-risk gene mutations.

g. Excluding KMT2A partial tandem duplication (PTD).

h. Complex karyotype:  $\geq 3$  unrelated chromosome abnormalities in the absence of other class-defining recurring genetic abnormalities; excludes hyperdiploid karyotypes with three or more trisomies (or polysomies) without structural abnormalities.

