i. Monosomal karyotype: presence of two or more distinct monosomies (excluding loss of X or Y), or one single autosomal monosomy in combination with at least one structural chromosome abnormality (excluding corebinding factor AML).

j. For the time being, these markers should not be used as an adverse prognostic marker if they co-occur with favorable-risk AML subtypes.

k. TP53 mutation at a variant allele fraction of at least 10%, irrespective of the TP53 allelic status (mono- or biallelic mutation); TP53 mutations are significantly associated with AML with complex and monosomal karyotype.

Of note, two “Adverse” genetic abnormalities in ELN 2022 risk stratification, t(8;16)(p11;p13)/KAT6A::CREBBP and t(3q26.2;v)/MECOM(EVI1)-rearranged, were not collected in this study at the planning of the study design.

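### SAP 5.2.1 applies an exception-free ELN risk order that contradicts the footnotes to its own Tables 5-2 and 5-3 in two cases

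*SAP*

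**What the plan says.** SAP section 5.2.1 sets out one stepwise list and uses it for both ELN versions.

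- **Step 1:** any favorable abnormality gives Favorable, with the comment "That is, Favorable genetic abnormalities always took precedence".
- **Step 2:** "Then, if he/she has any adverse genetic abnormality (cytogenetic or molecular genetic", the subject is Adverse.
- **Step 3:** any intermediate abnormality gives Intermediate.
- **Step 4:** with no genetic assessment at all the category is Missing; otherwise it is Intermediate.

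The tables that follow carry footnotes on co-occurring lesions.

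- Table 5-2 (ELN 2017) footnote d and Table 5-3 (ELN 2022) footnote f are attached to t(9;11)(p21.3;q23.3) in the Intermediate row. Both say that its presence "takes precedence over rare, concurrent adverse-risk gene mutations".
- Table 5-3 footnote d, attached to the mutated-NPM1 entries, says "AML with NPM1 mutation and adverse-risk cytogenetic abnormalities are categorized as adverse-risk". Table 5-2 has no such footnote.
- Table 5-3 footnote j says of a list of mutated genes that "these markers should not be used as an adverse prognostic marker if they co-occur with favorable-risk AML subtypes". Table 5-2 footnote g says the same of RUNX1 and ASXL1.

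Section 2.3.2 plans to tabulate "Details on AML diagnosis (initial diagnosis, ELN 2017 risk classification" among other items, and section 2.3 states that "demographics and other baseline characteristics will be summarized by dose level of MBG453" and for all subjects.

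**The concern.** A derivation rule exists so that two programmers working from the same data reach the same category. Here the rule and the footnotes give different categories for the same subject.

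The two conflicts have different causes. The t(9;11) conflict arises because step 2 comes before step 3 and catches any molecular adverse finding. The NPM1 conflict arises because step 1 comes first and admits no exception.

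They also push in opposite directions. Coding t(9;11) as Adverse makes the enrolled population look higher-risk by one category. Coding NPM1 with adverse cytogenetics as Favorable makes it look lower-risk by two.

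In a single-arm trial judged against a fixed 50% CR rate, readers use the baseline prognostic mix to interpret the observed rate, so the risk table should follow the classification it names. Footnote a to both tables also asks for response rates and outcomes by risk category, and section 2.2.1 leaves room for exploratory subgroups later.

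**Working it through.** The plan gives no figure to reproduce, so the check is a trace of the rule against the footnotes.

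**Test profiles**

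Except where stated, no other favorable lesion is present.

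| Profile | ELN version | Step that fires | SAP category | Footnote category |
|---|---|---|---|---|
| t(9;11) + adverse gene mutation (e.g. TP53), no other adverse cytogenetics | 2017 | 2 | Adverse | Intermediate (Table 5-2 d) |
| Same | 2022 | 2 | Adverse | Intermediate (Table 5-3 f) |
| Mutated NPM1, no FLT3-ITD, + adverse cytogenetics (e.g. -7) | 2022 | 1 | Favorable | Adverse (Table 5-3 d) |
| Mutated NPM1, FLT3-ITD present, + adverse cytogenetics | 2022 | 2 | Adverse | Adverse: agrees |
| Mutated NPM1, no or low FLT3-ITD, + adverse cytogenetics | 2017 | 1 | Favorable | No footnote: no conflict |
| Favorable lesion + RUNX1 or ASXL1 mutation only | both | 1 | Favorable | Favorable (5-2 g, 5-3 j): agrees |

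**Enumeration**

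Cross NPM1 (mutated, wild type), FLT3-ITD, adverse cytogenetics (no, yes), t(9;11) (no, yes) and adverse gene mutation (no, yes). t(9;11) is not counted under the adverse t(v;11q23.3)/KMT2A-rearranged entry.

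- *ELN 2017*, FLT3-ITD none, low or high: 2 × 3 × 2 × 2 × 2 = 48 profiles. Four NPM1/FLT3-ITD combinations are not favorable: mutated with high, and wild type with none, low or high. With t(9;11), an adverse gene mutation and no other adverse cytogenetics, they give 4 conflicts. Wild-type NPM1 with FLT3-ITD high is itself an adverse entry, so with t(9;11) and no further mutation it adds 1. Total: 5 of 48, all coded Adverse against Intermediate.
- *ELN 2022*, FLT3-ITD no or yes: 2 × 2 × 2 × 2 × 2 = 32 profiles. Mutated NPM1 without FLT3-ITD plus adverse cytogenetics gives 2 × 2 = 4 conflicts (Favorable against Adverse). Three combinations are not favorable: mutated with FLT3-ITD, and wild type with or without it. With t(9;11) and an adverse gene mutation only, they give 3 (Adverse against Intermediate). Total: 7 of 32.

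These count marker profiles, not subjects, and say nothing about frequency.

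**Effect of one miscoded subject**

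SAP section 1 reports that "a total of 85 patients were enrolled and treated at 800 mg MBG453". The Protocol Amendment 5 rationale gives 90 enrolled. Assuming all 90 were treated, 90 − 85 = 5 received 400 mg. One subject then moves a cell by:

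- 800 mg column: 100/85 = 1.18 points
- All subjects column: 100/90 = 1.11 points
- 400 mg column: 100/5 = 20.0 points

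**The case against.** The best defence is that the footnotes belong to the tables, the tables define what the steps mean by favorable, adverse and intermediate, and so the exceptions are already built in. For NPM1 this cannot be squared with the word *always* in step 1. For t(9;11) it is more plausible, because step 2 has no such word. But step 2 takes any adverse finding, molecular ones included, and the footnotes that exempt adverse gene markers (g in Table 5-2, j in Table 5-3) do so only alongside favorable-risk subtypes, which t(9;11) is not. At best the text is ambiguous. No derivation code is in the documents; it may already honour the footnotes, but then the SAP text is still wrong.

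Several limiting points stand.

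- The number of affected subjects is unknown, and the footnotes call the adverse mutations concurrent with t(9;11) rare. Nothing comparable is said of the NPM1 combination.
- The ELN 2017 table is the only visible planned output that carries a conflict, and it carries only the t(9;11) one. Redacted sections may use ELN 2022, but that cannot be seen.
- Footnote b to each table tempers the prognostic reading: impact is treatment-dependent (2017), and the marked ELN 2022 entries rest mainly on intensively treated patients, unlike this population. That weakens interpretation, but it does not excuse a category that departs from the cited scheme.
- In ELN 2022, limiting the NPM1 conflict to subjects without FLT3-ITD holds only if no other favorable lesion is present. With bZIP CEBPA, for example, step 1 again gives Favorable while footnote d gives Adverse.
- One of the five ELN 2017 conflicts treats wild-type NPM1 with FLT3-ITD high as a gene mutation. If it is not, the count is 5 − 1 = 4.

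**Conclusion.** The concern holds. As written, section 5.2.1 contradicts the SAP's own footnotes for t(9;11) with adverse gene mutations (both ELN versions), and for mutated NPM1 without FLT3-ITD plus adverse cytogenetics (ELN 2022 only). The first puts subjects in the wrong row of a planned baseline table; the second miscodes a derived variable by two categories.

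The consequence is confined to descriptive risk summaries and any exploratory subgroup added later. Section 2.2.1 pre-specifies no subgroup, and the CR analysis does not use ELN risk. It should be corrected before the final tables are produced, but it does not threaten the trial's main conclusion.

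The conflict itself follows from the text alone. The per-subject shifts rest on the assumption that all 90 enrolled subjects were treated.

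**What to change.** Amend section 5.2.1 in three places.

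1. Before step 1, add: *ELN 2022 only: NPM1 mutation with any adverse-risk cytogenetic abnormality = Adverse.* Taken literally, as footnote d is worded, this also overrides a co-occurring core-binding-factor or CEBPA lesion; the SAP should say whether that is intended.
2. Between steps 1 and 2, add: *ELN 2017 and ELN 2022: t(9;11)(p21.3;q23.3) with adverse findings limited to gene mutations = Intermediate.* State that t(9;11) is never counted under the adverse t(v;11q23.3)/KMT2A-rearranged entry, which it would otherwise match literally. State also whether, in ELN 2017, wild-type NPM1 with FLT3-ITD high counts as a gene mutation here.
3. Qualify the precedence sentence in step 1 so that favorable lesions take precedence except as stated in these two rules.

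Counting that FLT3-ITD entry as a gene mutation, the amended order resolves all 5 + 7 conflicting profiles and changes no other profile in the enumeration.

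The cost is three wording changes and two ordered conditions in the derivation program, with no new data. The two ELN 2022 adverse abnormalities that the SAP already reports as not collected remain a disclosed gap. If the program already applies the footnotes, only the text needs to change.

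### SAP 5.2.1 step 4 labels a subject Intermediate ELN risk when one of the two genetic assessments is absent and the other shows no classifying lesion

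*SAP*

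**What the plan says.** SAP 5.2.1 applies its rules in order. Step 1 assigns Favorable and step 2 assigns Adverse. Each is triggered by a single qualifying lesion from either source; step 2, for example, reads "Then, if he/she has any adverse genetic abnormality (cytogenetic or molecular genetic"). Step 3 does the same for Intermediate. Step 4 handles whoever is left. Its condition for Missing is "Then, if he/she has no cytogenetic and molecular genetic assessments", and it continues "risk will be assigned; Otherwise, an" Intermediate label for the rest. No step mentions a subject who has only one of the two assessments.

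Tables 5-2 (ELN 2017) and 5-3 (ELN 2022) define the classes. Intermediate is largely what remains after the other classes are excluded; one ELN 2017 row is "Cytogenetic abnormalities not classified as favorable or adverse". Adverse lesions come from both sources. Table 5-3 lists gene mutations such as "Mutated ASXL1, BCOR, EZH2, RUNX1, SF3B1, SRSF2, STAG2, U2AF1, or ZRSR2" next to complex or monosomal karyotype and losses of chromosomes 5, 7 and 17. Favorable lesions also come from both: NPM1 and CEBPA mutations on one side, t(8;21) and inv(16) on the other.

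In the visible text, ELN risk is used in two places. SAP 2.3.2 tabulates ELN 2017 risk at baseline in the FAS, and SAP 2.10 lists the ELN category among the items for the safety review meetings. SAP 2.2.1 plans no subgroups but allows exploratory ones to be added.

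**The concern.** A class reached by exclusion can be assigned only when the exclusion has been carried out. With no molecular result, a TP53, RUNX1 or ASXL1 mutation has not been ruled out. With no karyotype, a complex karyotype or a core-binding-factor lesion has not been ruled out. Step 4 then gives a substantive risk label where the data are incomplete. This is a missing-data rule and is separate from the order in which steps 1 to 3 rank observed lesions.

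The accuracy of the baseline description is what is at stake. The trial has one arm and a fixed 50% null value taken from external data, so readers will look at the risk mix when they judge what population was treated. The rule can only raise the Intermediate count, and it leaves a Missing row that counts only subjects with neither assessment.

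**Working it through.** The plan gives no figure to reproduce here. The check is to apply the four steps as written.

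**Step A: the rule.** Take a subject with no listed lesion, so that steps 1 to 3 do not fire, and vary which assessments exist. The condition in step 4 can be read as neither assessment done (plain reading) or as not both done (looser reading). The last column shows the result after the change proposed below.

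| Cytogenetics | Molecular | Plain reading | Looser reading | After the fix |
|---|---|---|---|---|
| done | done | Intermediate | Intermediate | Intermediate |
| done | absent | Intermediate | Missing | Missing/Not classifiable |
| absent | done | Intermediate | Missing | Missing/Not classifiable |
| absent | absent | Missing | Missing | Missing/Not classifiable |

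The two middle rows are the point at issue. The two readings give different tables from the same data.

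**Step B: a second route.** Under ELN 2017, a subject with molecular results only, wild-type NPM1 and absent or low FLT3-ITD may already become Intermediate at step 3, because Table 5-2 lists that state in the Intermediate row. The same row requires that no adverse-risk lesion be present, which cannot be shown without a karyotype. The label is as unsupported as under step 4.

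**Step C: the scale.** The documents do not say how many subjects lack one component, so the number affected, k, is an assumption. The shift in the Intermediate share is 100 × k / N. N is 90 for all enrolled subjects (protocol, Amendment 5 rationale) or 85 for those treated at 800 mg (SAP section 1).

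| k (assumed) | N = 90 | N = 85 |
|---|---|---|
| 1 | 1.1 points | 1.2 points |
| 5 | 5.6 points | 5.9 points |
| 10 | 11.1 points | 11.8 points |
| 20 | 22.2 points | 23.5 points |

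**Step D: reach.** SAP 2.5.2 bases success on a Beta(1,1) posterior for the CR rate in all FAS subjects assigned to 800 mg, with no covariate. SAP section 3 sizes the trial on the same rule. Neither uses ELN risk, so no value of k changes the decision, the sample size or the error rate.

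**The case against.** The strongest reply is that little depends on the label. No planned efficacy or safety analysis is split by ELN risk, the visible text plans no comparison of the ELN mix with historical patients, and the 50% benchmark is stated without a risk mix. All of this stands and sets the weight of the point.

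The wording is also loose enough to mean that not both assessments were done, which would send the middle rows of the table to Missing. That reading is possible but strained. If it is the intended one, step 4 still needs rewording, because two programmers could code it differently.

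Three stronger readings are tempting, and the documents do not support them:

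- **A count of misfiled Adverse subjects.** A reader might assume that 10–20% of 90 subjects lack one component and that 40–60% of those are truly Adverse, giving 90 × 0.10 × 0.40 = 3.6 to 90 × 0.20 × 0.60 = 10.8. Neither rate is in the documents. The product also overcounts, because step 2 already captures anyone whose adverse lesion shows in the available component. Cytogenetics is a scheduled screening assessment (protocol Table 8-1), and redactions prevent a judgement on molecular completeness.
- **That missing genetics would be concealed.** SAP 2.3.2 tabulates cytogenetic abnormalities separately, and SAP 2.1 provides for a missing category where applicable. At least the cytogenetic gap should be visible.
- **That the two uncollected ELN 2022 lesions are an instance of this fault.** The SAP says openly that they "were not collected in this study at the planning of the study design". That gap applies to every subject and concerns ELN 2022 only. It is not a case of one assessment being absent for a particular subject.

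**Conclusion.** On its plain reading, step 4 assigns Intermediate to subjects whom the SAP's own tables cannot place. This is a stated rule that produces an unsupported label, and it is worth correcting. Its weight is modest. It affects the baseline ELN table and any ELN subgroup added later, and does not touch the primary CR conclusion. The size depends on how many subjects have one assessment missing and no classifying lesion in the other. The documents do not give that number, and if it is zero nothing changes. The direction in the Intermediate row is certain, but the share of relabelled subjects who are truly Adverse or Favorable cannot be derived from the documents.

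**What to change.** Reword step 4 so that a subject with either assessment missing or not evaluable, and no decisive lesion in the available one, is assigned Missing/Not classifiable. Let the default Intermediate apply only when both assessments are evaluable.

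Define a decisive lesion as one whose label the missing component could not overturn under the tables' footnotes:

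- Keep Intermediate for t(9;11) when molecular results are absent, because note d of Table 5-2 and note f of Table 5-3 give it precedence over rare concurrent adverse-risk mutations. A blanket requirement for both assessments would wrongly remove this label.
- Under ELN 2022, treat mutated NPM1 without a karyotype as not classifiable, because note d of Table 5-3 makes it Adverse when adverse cytogenetics are present.
- State how a RUNX1 or ASXL1 mutation without a karyotype is handled, because note g of Table 5-2 and note j of Table 5-3 set these markers aside when a favorable subtype co-occurs.
- Do not count rows that depend on exclusion, such as the wild-type NPM1 row of Table 5-2, as decisive at step 3 when the karyotype is missing.

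Tabulate missingness by component (cytogenetic, molecular, both) for ELN 2017 and ELN 2022.

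The cost is a few lines of SAP text and derivation code, with no new data. The small downside is a larger Missing/Not classifiable row.
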